#### 4.5 Multiple Comparisons

Because of the exploratory nature of this study, there will be no adjustment for multiple comparisons.

#### 4.6 Data Derivations and Transformations

The following derivations will be used in this study:

Study Day:

- Date of assessment – 1st date of study drug administration + 1 for assessments done on or after the 1st date of study drug administration
- Date of assessment – 1st date of study drug administration for assessments done before the 1st date of study drug administration

Baseline Observation: the last non-missing value prior to the 1st study drug administration.

Duration:

- Duration in days = end date – start date + 1
- Duration in minutes = end time in minutes – start time in minutes

Origin or Start Date for Time to Event Endpoints:

- Time to Clinical Response: date of 1st study drug administration
- Time to Hospital Discharge: date of 1st study drug administration
- Time to Sustained Normalization of Temperature: date of 1st study drug administration
- Time to Clinical Progression: date of 1st study drug administration

Event Date for Time to Clinical Response and time to sustained normalization of temperature:

- If a subject met the criteria for clinical response or sustained normalization of temperature at multiple assessments, the date of the first assessment meeting the definition of clinical response or sustained normalization of temperature will be used as the event date for deriving time to clinical response or sustained normalization of temperature.

Event Date for Time to Clinical Progression

- The event date will be the date of death, the start date of mechanical ventilation, or the date of ICU admission, whichever occurs first.

## 5. STUDY SUBJECTS

### 5.1 Disposition of Subjects

A table of frequency counts and percentages of all subjects who are screened, randomized, and in each analysis population will be provided. Subject disposition including study completion status and reasons for early termination will be tabulated by treatment group and overall. A by subject listing will be provided.

### 5.2 Protocol Deviations

Distribution of the types of protocol deviations and the number of subjects that deviate from the protocol will be tabulated for the treatment groups in the ITT population. Protocol deviations will also be tabulated by severity (e.g., minor or major). A listing of all protocol deviations will be provided.

### 5.3 Demographic Characteristics

Descriptive statistics will be used to summarize the demographic characteristics (age, gender, race, ethnicity, height, weight, and Body Mass Index [BMI]) for the ITT population. A by subject listing will be provided.

### 5.4 Baseline Characteristics

Baseline characteristics of ITT subjects including historical SARS-CoV-2 results and pregnancy test will be listed and tabulated if appropriate.

## 5.5 Medical History

All medical conditions will be classified by system organ class (SOC) and preferred term (PT) using the Medical Dictionary for Regulatory Activities (MedDRA). The number and percent of subjects with each medical condition will be presented for each SOC and PT for the ITT population.

## 5.6 Concomitant Medications

All concomitant medications collected will be coded using the World Health Organization (WHO) Drug Dictionary. The number and percent of ITT subjects using concomitant medications will be tabulated by Anatomical, Therapeutic, and Chemical (ATC) level 2 and by ATC level 4. If the ATC level 2 or 4 term is missing, the higher ATC level term will be used in the medication summary table and data listing.

Prior medications will be summarized separately from concomitant medications, for the overall ITT population.

Prior medications are defined as medications that ended prior to the date of 1st study drug administration. Concomitant medications are defined as medications that started at any time but ended on or after the date of 1st study drug administration, including those that are ongoing at study completion. In the case of a missing or partial end date/time, in order to determine whether a medication is prior or concomitant, the following conservative imputation rule will be used: the unknown portions of a medication end date/time will be imputed to the latest possible. The imputed medication end date/time will then be compared with the date of 1st study drug administration to determine if the medication is prior or concomitant.

Note the imputed end date/time will only be used to determine whether a medication is prior or concomitant. The actual date/time reported on the electronic case report forms (eCRFs) will be presented in the listings.

All concomitant medications collected will be reviewed in a data review meeting conducted prior to database lock. ATC or Preferred terms for COVID-19 specific, potentially disease modifying medications will be identified by the study team. Subsequently, a tabular summary by treatment group of these COVID-19 specific concomitant medications based on the identified ATC or preferred terms will be generated. If clinically important imbalance was observed in the use of these medications between the 2 treatment groups, additional supplemental efficacy analyses may be performed in a post-hoc manner to adjust for the difference(s) in such medication use.

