The primary efficacy analysis will be carried out on the ITT population and repeated on the PP population (if different from the ITT population) by Fisher's exact test. Secondary and exploratory efficacy analyses will be analyzed by means of Kaplan-Meier survival estimates and curves and compared between treatment groups by means of the Log-rank test for time to event variables, analysis of covariance (ANCOVA) when adjusting for covariates, or analysis of variance (ANOVA) when without covariates for normally-distributed variables or Wilcoxon rank-sum test for non-normally-distributed variables. Detailed data handling and evaluation procedures and details of the interim review will be described in the Statistical Analysis Plan (SAP).

For the primary endpoint, if the value of the subject is missing, then a conservative imputation rule will be used such that the subject will be treated as having met the condition for the primary efficacy analysis. The choice of analysis method for primary, secondary and exploratory efficacy endpoints will be described in detail in the SAP which will be finalized and signed off before data analysis is performed.

The SAP may include exploratory analyses of various aspects of SMT inclusive of different interventional strategies and evolving treatment modalities. Grifols will analyze the use of COVID-19 specific, potentially disease modifying treatments for any potential differences between study arms. This analysis will be fully detailed in the SAP since medical understanding of COVID-19 interventions is rapidly evolving. For ethical reasons, there are no restrictions placed on what are perceived to be potentially life-saving therapies (apart from participation in another interventional clinical trial).

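### The by-arm table of COVID-19 specific drugs (SAP 5.6) omits courses finished before the first infusion and mixes therapy already running with drugs started after dosing

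*SAP*

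**What the plan says.** SAP 5.6 sorts medications by end date relative to first study drug. For the earlier group: "Prior medications are defined as medications that ended prior to the date of" first administration. For the rest: "Concomitant medications are defined as medications that started at any time but ended on or after the date of" first administration, with ongoing drugs included. For missing or partial end dates, "the unknown portions of a medication end date/time will be imputed to the latest possible".

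The two groups are then reported differently. For the earlier group, "Prior medications will be summarized separately from concomitant medications, for the overall ITT population". For COVID-19 specific drugs, the study team identifies the relevant terms at a data review meeting, after which "a tabular summary by treatment group of these COVID-19 specific concomitant medications based on the identified ATC or preferred terms will be generated". If that table shows a clinically important imbalance, "additional supplemental efficacy analyses may be performed in a post-hoc manner to adjust for the difference(s) in such medication use".

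Protocol 9.1 states the commitment more broadly: "Grifols will analyze the use of COVID-19 specific, potentially disease modifying treatments for any potential differences between study arms". It leaves the detail to the SAP.

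**The concern.** The by-arm table exists to show whether the arms differed in other treatments that could change outcome. As written, it draws its line in an unhelpful place, in two ways.

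First, a single-dose or short-course drug completed the day before the infusion is left out, while the same drug given on the infusion date is counted. Completed courses cannot be a consequence of study drug, so they are sound covariates for adjustment.

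Second, the table puts therapy already running at first infusion together with drugs started later. Later drugs may be given because of how the patient fared on study treatment. An adjustment built on the pooled table could condition on post-randomization drug use and remove part of a treatment effect or distort it.

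At stake are how well the planned check of background therapy can be interpreted and whether the SAP delivers what Protocol 9.1 promises. The primary test itself is not at stake.

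**Working it through.** The plan gives no figure to reproduce here: there is no usage rate, event rate or power calculation. The check is a reading of the definitions, followed by a scale check on assumed inputs.

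**1. Apply the SAP 5.6 definitions course by course.**

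- Started and ended before the first-dose date, end date known: prior, so not in the COVID-19 by-arm table.
- Started before Day 1, ended on the first-dose date or later: in the table.
- Started before Day 1 and ongoing: in the table.
- End date missing, or partial with a latest possible value on or after the first-dose date: in the table.
- Started after the first dose: in the table, not separated from the three groups above.

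Only the first group is lost. The other four share one display.

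**2. Look for another place that covers the lost group.** SAP 5.4 does not name COVID-19 therapy among baseline characteristics. The prior-medication summary in SAP 5.6 is for the overall ITT population. SAP 5.1 and 7.2.1 name treatment group and overall side by side when both are wanted, which favours a pooled reading. SAP 4 makes summaries by treatment group the default, which favours a split reading. On either reading, that summary is not restricted to COVID-19 drugs, and the imbalance check does not refer to it.

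**3. Ask whether the lost group can exist.** Protocol 5.1 limits screening to 48 hours after admission but accepts symptoms of any duration, so treatment before admission is possible. Protocol 6.2.1 bars only commercial AAT before entry. Protocol 7.2.2 allows for a delayed first infusion. Neither Protocol 4.3.2 nor SAP 3.2.1 states a stratification factor.

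**4. Scale check.** From the documents: about 100 subjects randomized 1:1, so n = 50 per arm. Assumed: prevalence p of completed pre-infusion use, a 30% primary event risk, and a drug that halves it to 15%.

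Chance of a gap between arms, with X1 and X0 independent Bin(50, p):

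| p | SD of gap, √(2p(1−p)/50) | gap ≥ 10 points (5 subjects) | gap ≥ 16 points (8 subjects) | gap ≥ 20 points (10 subjects) |
|---|---|---|---|---|
| 5% | 4.4 points | 3.9% | 0.1% | <0.01% |
| 10% | 6.0 points | 13.1% | 1.3% | 0.2% |
| 20% | 8.0 points | 25.9% | 6.0% | 1.7% |
| 30% | 9.2 points | 32.6% | 10.1% | 3.8% |

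Shift in the primary risk difference = gap × (0.30 − 0.15):

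- 10-point gap: 0.10 × 0.15 = 0.015, or 1.5 points
- 16-point gap: 0.16 × 0.15 = 0.024, or 2.4 points
- 20-point gap: 0.20 × 0.15 = 0.030, or 3.0 points

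If the drug lowers risk by only 5 points, the 10- and 20-point gaps give 0.5 and 1.0 points.

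Standard error of the primary difference at 30% per arm: √(2 × 0.30 × 0.70 / 50) = 0.092, or about 9 points. The 1.5-point shift is 1.5/9.2 = 0.16 standard errors, and the 2.4-point shift is 2.4/9.2 = 0.26.

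**The case against.** A reader might infer that imbalance in baseline COVID-19 therapy as a whole would go unseen. The documents do not support that. Therapy begun before Day 1 and still running is compared by arm, and doubtful end dates are pushed into the table. With screening within 48 hours of admission and infusion meant to follow quickly, most multi-day hospital courses would cross Day 1. Completed courses may also be visible elsewhere: the reference to the overall ITT population may only name the analysis set, SAP 4 makes by-arm summaries the default, and listings are sorted by treatment group. All of this stands, and it confines the point to courses completed before the first-dose date and to the pooling.

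The review step may also be broader than it looks. SAP 5.6 says "All concomitant medications collected will be reviewed in a data review meeting conducted prior to database lock", and since prior drugs are derived from the same collected records, that phrase may mean the whole medication data set. This is plausible, but the table that follows still says concomitant, a term the same section defines.

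The Protocol 9.1 sentence sits in a paragraph about standard medical treatment and defers to the SAP, so a focus on concomitant use can be defended as elaboration. The departure is therefore a narrowing without a stated reason, not a flat contradiction.

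Finally, the follow-up analysis is optional and post hoc with no threshold, so nothing forbids using prior drugs in it. That is true, but the written rule would not prompt it.

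**Conclusion.** The point holds as a minor gap in SAP 5.6. Completed COVID-19 courses with a known end date before the first infusion enter neither the COVID-19 specific by-arm table nor the imbalance check, and the table cannot separate pre-infusion therapy from drugs started after dosing. This is narrower than the Protocol 9.1 commitment.

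It would be wrong to go further and say that the primary result is biased. Chance imbalance after randomization is already covered by the test's error rate and the confidence interval. The likely shift is small: about 1.5 points for a 10-point gap, against a standard error of about 9. Larger gaps shift it more but are rarer. The prevalences, the 30% event risk and the halving are all assumptions, as the documents give none of them. The change is worth making because it is cheap, not because the trial's conclusion depends on it.

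**What to change.** In SAP 5.6, build the COVID-19 specific table by treatment group from all recorded medications, in two panels:

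1. started before the first infusion, whether completed or ongoing;
2. started after the first infusion.

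Base any imbalance-triggered supplemental adjustment on panel 1 only, and keep panel 2 descriptive. State that the data review meeting covers prior as well as concomitant records, and that the general prior-medication summary is by treatment group.

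The split needs a rule for starts on the infusion date and for partial start dates, because SAP 5.6 gives an imputation rule for medication end dates only.

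The cost is SAP wording, one extra panel and slightly more coding review before database lock. The panel can show only the records and dates that the eCRF collects. Protocol 6.2 asks for concomitant medications and states no look-back period, so treatment before admission may be incompletely captured, and the table should carry a footnote saying so.

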## 6. EFFICACY ANALYSES

All efficacy analyses will be carried out using the ITT population. Data on all efficacy endpoints will be listed and tabulated if appropriate.

### 6.1 Primary Efficacy Endpoint and Analysis

The primary efficacy analysis will be carried out on the ITT population. If there is difference between the PP population and ITT population, the analysis will be repeated using the PP population.

The primary efficacy variable is the proportion of subjects who die or require ICU admission on

or before Day 29, or who are dependent on high flow oxygen devices or invasive mechanical ventilation on Day 29. The primary efficacy endpoint will be derived based on the subject status (Alive/Death), ICU admission, mechanical ventilation and oxygen administration recorded in the database. Subjects who met any of the criteria listed below will be treated as meeting the primary efficacy endpoint:

- 1) Death is recorded on the eCRF All Visits page “General Duration of Hospitalization, & Overall Requirement for Mechanical Ventilation, ICU Admission and/or Oxygen Supplementation”;
- 2) ICU admission date is recorded on the eCRF All Visits page “General Duration of Hospitalization, & Overall Requirement for Mechanical Ventilation, ICU Admission and/or Oxygen Supplementation”;
- 3) On the eCRF Day 29 page “Mechanical Ventilation and Oxygen Administration”:
  - a. subject on mechanical ventilation is recorded in the mechanical ventilation record for that day, i.e., “Is the subject on a ventilator?” is recorded as “Yes”;
  - Or
  - b. the modality of oxygen administration is recorded as “High flow oxygen devices”

If for a subject any of the 4 criteria above could not be assessed due to missing data, then the subject will be treated as meeting the endpoint in the primary efficacy analysis.

The null hypothesis is that there is no difference in the proportions of subjects who met the primary endpoint between randomized groups;  $H_0: \pi_t - \pi_c = 0$ . The alternative hypothesis is that the proportions of subjects who met the primary endpoint are different between the treatment groups;  $H_1: \pi_t - \pi_c \neq 0$ .

The proportion of subjects who met the criteria for the primary endpoint within each treatment group will be presented along with a two-sided exact (Clopper-Pearson) 95% confidence interval (CI).

The observed difference in the proportion of subjects meeting the criteria between treatment groups along with the exact unconditional 95% CI for risk difference will be calculated. The null hypothesis will be tested using Chi-square statistic and the p-value will be reported.

Subgroup analyses of the primary efficacy endpoint by baseline characteristics such as age group (with age cutoffs defined either by absolute values or by a summary metric [e.g., median] of the observed baseline values) and gender will be performed using the analysis method described above, if appropriate.

If for one or more subjects the actual treatment received is different from the randomized treatment and if deemed necessary, sensitivity analysis of the primary efficacy endpoint will be performed by repeating the primary efficacy analysis as described above in this section, but with subjects grouped according to the actual treatment received instead of the randomized treatment.

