5.3.4 Follow-up of Subjects Withdrawn from Study

For subjects administered any amount of blinded Liquid Alpha₁-PI (Human) or blinded placebo who withdraw from the clinical trial prior to Day 29, study procedures and assessments scheduled for the Day 15 Visit will be performed at the time of withdrawal, during an unscheduled visit. In addition, to assure major clinical outcomes are adequately captured as a measure of overall safety, these subjects will be asked to return for their chronological Day 29 Clinic Visit (ie, 28 days after Day 1 baseline), provided that they or their legally acceptable representative have not withdrawn consent. At the chronological Day 29 Clinic Visit, all assessments will be performed *except for* central laboratory testing: cytokine panel, levels of alpha 1-PI (AAT) activity and antigen, respiratory sample for quantitative measurement of SARS-CoV-2 viral load (obtained via nasopharyngeal swab), and quantitative measurement of IgM and IgG antibodies, *which are not required for these subjects at chronological Day 29 for premature withdrawals*. Note: A Day 29 Clinic Visit would not be necessary if the unscheduled visit is within 4 days of the subject's chronological Day 29 visit because the assessments/outcome measures would be the same and would not need to be repeated in such a short a time interval.

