7.2.5 Day 15±1 day Mandatory for All Subjects

Assessments include the following:

- Ordinal Scale assessment
- NEWS ([Appendix 2](#))
- Clinical features key symptoms: fever, cough, shortness of breath, fatigue, myalgia etc.
- Vital signs (temperature, systolic and diastolic blood pressure, pulse, respiratory rate)
- Record any supplemental oxygen administration (type, %, flow start/end date/time)

GRIFOLS Bioscience Industrial Group			
Number	Version	Status	Effective Date
GC2006-A Multicenter, Randomized, Open-label, Parallel Group Pilot Study to Evaluate the Safety and Efficacy of Prolastin®-C Liquid plus Standard Medical Treatment (SMT) versus SMT alone in Hospitalized Subjects with COVID-19	6.0	Effective	08-Dec-2021
55 of 94			

 If subject requires mechanical ventilation post randomization: Record mechanical ventilation (start/end date/time) Record oxygen saturation (specify on or off oxygen supplementation) Record SAEs and TEAEs Record standard care concomitant medications Respiratory sample for quantitative measurement of SARS-CoV-2 viral load by NAT or PCR (real-time RT-PCR) (obtained via nasopharyngeal swab) Sample for quantitative measurement of IgM and IgG antibodies to SARS-CoV-2 (if antibodies cannot be determined at the site store serum samples frozen at -70°C for later analysis at an external lab) Serum Chemistry (creatinine, albumin, ALT, total bilirubin, LDH) Calculate eGFR using the Cockcroft-Gault formula. Hematology absolute neutrophil & lymphocyte count and standard hematology (hemoglobin, hematocrit, platelet count, leukocyte count with differential) Assessment of ARDS (Berlin Criteria) (Appendix 3) Ferritin, D-dimer, CRP Cytokine panel (IL-1β, IL-10, IL-6, IL-8, IL-2, interferon γ, and TNF-α). Note: serum samples must be stored at -70° C for later analysis at a reference laboratory. Levels of alpha 1-PI (AAT) activity and antigen; both plasma (sodium citrate) and serum samples to be stored at - 70° C for measurement of both antigenic content and functional activity (potency). 			

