### 2.2.2 Secondary Efficacy Endpoints

The secondary efficacy endpoints include the following:

- Assessment of Clinical Severity: Change in NEWS from baseline (Day 1 through Day 29).  
The NEWS has demonstrated an ability to discriminate patients at risk of poor outcomes. This score is based on 7 clinical parameters (respiration rate, oxygen saturation, any supplemental oxygen, temperature, systolic blood pressure, heart rate, level of consciousness [Alert, Voice, Pain, Unresponsive]).
- Time to clinical response: NEWS  $\leq 2$  maintained for 24 hours, Day 1 through Day 29
- Time to hospital discharge: defined as duration of hospitalization from Day 1 through Day 29
- If admitted to ICU post randomization: Duration of ICU stay through Day 29
- Duration of any oxygen use Day 1 through Day 29
- If requiring mechanical ventilation post randomization: Duration mechanical ventilation through Day 29
- Absolute value and mean change from baseline in the Ordinal scale Day 1 through Day 29  
The Ordinal scale is as follows:
  - 1) Death;
  - 2) Hospitalized, on invasive mechanical ventilation or extracorporeal membrane oxygenation (ECMO);
  - 3) Hospitalized, on non-invasive ventilation or high flow oxygen devices;
  - 4) Hospitalized, requiring supplemental oxygen;
  - 5) Hospitalized, not requiring supplemental oxygen;
  - 6) Not hospitalized, limitation on activities;
  - 7) Not hospitalized, no limitations on activities.
- Proportion (percentage) of subjects in each severity category of the 7-point Ordinal scale at Day 15 and Day 29
- Time to sustained normalization of temperature and proportion of subjects with normalization of fever at all time points, defined as temperature  $<36.6$  °C armpit,  $<37.2$  °C oral, or  $<37.8$  °C rectal sustained for at least 24 hours
- Number of subjects who develop Acute Respiratory Distress Syndrome (ARDS) through

Day 29

- Length of time to clinical progression through Day 29 (defined as the time to death, mechanical ventilation, or ICU admission)

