#### **4.3 Assessment Windows**

Data will be summarized by nominal study visit recorded in the database.

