### **Ordinal scales**

- a) The absolute value and change from baseline in the Ordinal scale from Day 1 through Day 29 will be summarized by treatment group and visit using descriptive statistics.

Mean change in Ordinal scales through Day 29 will be evaluated by fitting a linear MMRM similar to the one described above for “assessment of clinical severity.”

- b) The proportion of subjects in each severity category of the 7-point Ordinal scale at Day 15 and Day 29 will be tabulated. The difference in severity category distribution between treatment groups at Day 15 and Day 29 will be examined using proportional-odds cumulative logit model. The cumulative logits model will compare lower ordinal scales to higher ones, or equivalently, less favorable outcomes to more favorable ones. The model may be adjusted for baseline characteristics such as age and gender if appropriate. The estimated odds ratio and 95% CI will be presented. Graphical illustrations of the fitted model will also be presented for Day 15 and Day 29.

The proportional odds assumption will be tested using a score test at the two-sided alpha level of 0.05. If the proportional odds assumption is not satisfied, given the anti-conservative nature of the score test, the proportional odds model will still be used for the analysis, and the results will be presented along with the score test p-value to help put these results in context. If the proportion odds assumption is rejected or if the proportional odds model fails to converge, a sensitivity or alternative analysis using a non-parametric Wilcoxon Rank Sum test will be performed. The p-value from Wilcoxon Rank Sum test, as well as the Hodges-Lehmann estimate of the treatment difference and the corresponding

95% CI will be provided.

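### SAP 6.1 can score a documented Day 29 non-event as a primary-endpoint failure, because the withdrawal visit that the protocol accepts in place of Day 29 is not mapped to it, and no planned analysis varies the missing-data assumption

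*SAP*

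**What the plan says.** SAP 6.1 builds the primary endpoint from four criteria. Death and ICU admission come from the All Visits eCRF page. Mechanical ventilation and high-flow oxygen come from the Day 29 ventilation and oxygen page. For the primary analysis, if "any of the 4 criteria above could not be assessed due to missing data, then the subject will be treated as meeting the endpoint".

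Protocol 9.1 states its rule for the subject's endpoint value as a whole: "For the primary endpoint, if the value of the subject is missing, then a conservative imputation rule will be used". Protocol 9.5 leaves the detail of missing-data handling to the SAP.

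Other records bear on the same facts:

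- **Withdrawal visit.** For dosed subjects who withdraw before Day 29, protocol 5.3.4 says that "study procedures and assessments scheduled for the Day 15 Visit will be performed at the time of withdrawal". It adds: "A Day 29 Clinic Visit would not be necessary if the unscheduled visit is within 4 days" of the chronological Day 29. The Day 15 list in protocol 7.2.5 includes mechanical ventilation and this item: "Record any supplemental oxygen administration (type, %, flow start/end date/time".
- **Visit mapping.** SAP 4.3 says only: "Data will be summarized by nominal study visit recorded in the database".
- **Ordinal scale.** SAP 6.2 plans a separate Day 29 analysis: "The proportion of subjects in each severity category of the 7-point Ordinal scale at Day 15 and Day 29 will be tabulated". Category 3 reads "Hospitalized, on non-invasive ventilation or high flow oxygen devices" and category 2 covers invasive ventilation or ECMO, so categories 4 to 7 exclude both Day 29 states in the endpoint.

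For the primary endpoint the SAP plans a per-protocol repeat, age and gender subgroups, and a regrouping by treatment actually received. All use the same derivation.

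**The concern.** The missing-data rule acts on single criteria, and two of the four are tied to one eCRF page. The SAP does not say whether another record of the same status may be used when that page is absent or incomplete. Two kinds of subject are exposed:

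- **(a)** A subject withdraws, is examined within 4 days of Day 29 and is on neither a ventilator nor high-flow oxygen. The protocol asks for no further visit, so there may be no Day 29 page.
- **(b)** The Day 29 ventilation and oxygen page stays incomplete, but a Day 29 ordinal score of 4 to 7 is on file.

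Either can become an imputed event against the recorded evidence. With about 50 subjects per arm, a few such events dilute a real difference. If they fall unequally between arms, they can also create a difference. No planned output counts imputed events by arm or shows whether the primary conclusion depends on them.

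**Working it through.** **1. Do the SAP and protocol rules differ?** Let each of the four criteria be yes, no or missing: 3^4 = 81 patterns.

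- At least one yes: 81 − 2^4 = 65 patterns, an event under both rules.
- All four no: 1 pattern, a non-event under both rules.
- No yes and at least one missing: 16 − 1 = 15 patterns. The SAP scores an event. Because the endpoint is an 'or' composite, its value is unknown, so the protocol rule also imputes an event.

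On the four criteria alone the rules agree in all 81 patterns. They part only when a record outside the named page settles the status, or if a missing value is taken to mean that all four parts are missing (14 of the 15 patterns would then differ).

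**2. Case (a) under the text.** Protocol 5.3.4 accepts the early visit, and that visit records oxygen and ventilation. SAP 6.1 looks for both on the Day 29 page, and SAP 4.3 gives no mapping. The literal result is an unassessable criterion and an imputed event.

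**3. Size.** The documents give no event rate, effect size, power or missing rate, so there is no figure to reproduce and every rate below is an assumption. From the documents: about 100 subjects, 1:1, chi-square test, two-sided 5%. Let p be the true event rate, m the share of non-events with an unassessable criterion, and r the share of those that other records resolve:

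observed rate = p + (1 − p) × m × (1 − r)

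Rejection probabilities come from exact binomial enumeration of the uncorrected chi-square test over all 51 × 51 outcomes at 50 per arm.

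*Power, true rates 30% placebo v 10% active:*

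| m | r | Observed rates | Power |
|---|---|---|---|
| 0 | – | 30.0% v 10.0% | 73% |
| 2% | 0 | 31.4% v 11.8% | 68% |
| 2% | 0.5 | 30.7% v 10.9% | 71% |
| 5% | 0 | 33.5% v 14.5% | 62% |
| 5% | 0.5 | 31.75% v 12.25% | 67% |

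At m = 2% the affected subjects number 50 × (0.7 + 0.9) × 0.02 = 1.6 in the whole trial.

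*No true effect, 20% in both arms:*

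| Unassessable, active v placebo | r | Observed, active v placebo | All rejections | Favouring active |
|---|---|---|---|---|
| none | – | 20.0% v 20.0% | 5.2% | 2.6% |
| 2% v 4% | 0 | 21.6% v 23.2% | 5.5% | 3.9% |
| 5% v 10% | 0 | 24.0% v 28.0% | 7.5% | 6.7% |
| 5% v 10% | 0.5 | 22.0% v 24.0% | 5.7% | 4.3% |

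The part due to the missing source rule is the gap between r = 0 and r = 0.5, not the gap from m = 0.

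**The case against.** The case for leaving the text alone is substantial.

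- **Contradiction.** A reader might infer that the SAP contradicts protocol 9.1. It does not: the rules agree on the four criteria, and protocol 9.5 delegates the detail. This objection stands.
- **Page restriction.** It is inferred from how the criteria are defined. The missing-data sentence names no page, and SAP 6.1 also speaks of what is recorded in the database. Nothing forbids entering the 5.3.4 visit as Day 29. This stands as far as it goes: wrong scoring is a literal reading, not a stated outcome. But the text then permits two derivations of the primary endpoint.
- **Rarity.** Day 29 is mandatory after discharge, withdrawn subjects are asked back, and SAP 4.1 requires queries resolved before lock, so case (b) should seldom survive to the final analysis. This stands for the final analysis. The interim futility analysis uses the same 6.1 method, may use data with queries still open, and has no sensitivity analyses planned.
- **Existing outputs.** Listings will show the raw records, and time to clinical progression censors instead of imputing. True, but that endpoint omits Day 29 high-flow dependence, and listings do not test the conclusion.
- **Exploratory trial, blinded missingness.** The plan states no power, and a 2:1 imbalance in missingness is only an assumption in a double-blind trial. This limits the size of the point, not its logic.

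**Conclusion.** The point holds in a limited form. Followed literally, SAP 6.1 can override a known non-event. The clearest route is the withdrawal visit that protocol 5.3.4 accepts; an incomplete Day 29 page beside an ordinal score of 4 to 7 is a rarer one. In addition, no planned analysis varies the missing-data assumption for the primary endpoint, and worst-case imputation is not conservative if missingness is higher on placebo.

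The size is probably small: about 3 points of power at 2% unassessable with half resolvable, and 1.3 points more rejections favouring active under the 2% v 4% imbalance. Both rest wholly on assumed rates.

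A reader might take the fall from 73% to 62% at 5% missing as the cost of this gap. It is the cost of scoring missing as event, which both documents prespecify and which the fix keeps. Nor does the point reach a subject discharged and not seen since Day 15: a blank oxygen or ventilation restart there may simply be missing data, so that status stays unresolved.

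**What to change.** Before unblinding, add to SAP 6.1:

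1. A protocol 5.3.4 visit within 4 days of Day 29 supplies Day 29 ventilation and high-flow oxygen status. Death and ICU admission through Day 29 are still taken from the All Visits page.
2. A recorded Day 29 ordinal score of 4 to 7 may resolve a blank Day 29 ventilation or oxygen field. Category 3 does not, because it mixes non-invasive ventilation with high flow.
3. An event is imputed only for subjects still unresolved, which keeps the protocol 9.1 rule.

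Add one table: imputed events by arm, an observed-case repeat, and a simple tipping point with the imputed outcome varied separately by arm.

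The cost is SAP wording, one derivation and one table, with no new data collection and no protocol amendment. Two small carry-forward assumptions come with it. Status up to 4 days earlier is taken to hold at Day 29, which protocol 5.3.4 already accepts. The ordinal score, which the schedule takes at the first assessment of the day, is taken to hold for the rest of that day.
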